#### Other endpoints

Data for magnetization transfer ratio (MTR) recovery at EOS in new MTR lesions detected at Months 6 and 12 and normalized T1 intensity in SELs will be listed.

Actigraphy sub-study data will be collected and processed by an external vendor, Koneksa. Analysis and reporting of this sub-study will be performed separately from the CSR.

Missing data will not be imputed in the analysis of tertiary endpoints, nor will sensitivity or subgroup analyses be conducted.

#### 3.5 MULTIPLICITY ISSUES

To strongly control the Type 1 error rate for the study, a hierarchical testing procedure will be applied at a 2-sided 5% significance level, ie, each hypothesis will be formally tested only if the preceding one is significant at the 5% level. If statistical significance is achieved for the primary endpoint, a selective set of secondary endpoints will be tested following the hierarchical testing procedure shown below:

- Time to onset of 3-month CDP as assessed by the EDSS score
- Number of new and/or enlarging T2 hyperintense lesions per year
- Time to onset of sustained 20% increase in the 9-HPT for at least 3 months
- Time to onset of sustained 20% increase in the T25-FW for at least 3 months
- Time to onset of CDI confirmed over at least 6 months
- Percent change in brain volume as detected by MRI scans at the EOS compared to Month 6

#### 3.6 SAFETY ANALYSES

All safety analyses will be performed on the safety population as defined in Section 2, unless otherwise specified, using the following common rules:

- The analysis of the safety variables will be descriptive with no testing planned. The summary of safety results will be presented by treatment group.
- Safety data in participants who do not belong to the safety population (eg, exposed but not randomized) will be provided separately.

#### 3.6.1 Extent of exposure

The extent of IMP exposure will be assessed by the duration of IMP exposure and compliance and summarized within the safety population.

#### **Duration of IMP exposure**

Duration of IMP exposure is defined as last IMP administration date - first IMP administration date + 1 day, regardless of unplanned intermittent discontinuations. If the date of the last dose of IMP is missing, the duration of IMP will be left as missing.

Duration of IMP exposure will be summarized quantitatively and categorically in the DB treatment period and OL period respectively: >0 to  $\leq$ 24 weeks, >24 to  $\leq$ 48 weeks, >48 to  $\leq$ 72 weeks, >72 to  $\leq$ 96 weeks, >96 weeks.

Additionally, the cumulative duration of treatment exposure (expressed in participant-years) will be provided.

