7.1.2 Temporary discontinuation

Temporary intervention discontinuation, because of suspected AEs or disruption of the clinical trial due to a regional or national emergency declared by a governmental agency (Appendix 10 [Section 10.10]: Contingency measures for a regional or national emergency that is declared by a governmental agency) may be considered by the Treating Investigator. For all temporary intervention discontinuations, duration should be recorded by the Investigator in the appropriate pages of the eCRF.

If surgery is needed during the study, the benefit-risk of withholding the IMP for at least 3 to 7 days pre- and post-surgery and the risk of bleeding should be considered.

The following shall lead to temporary treatment discontinuation:

- Cytopenias: algorithm for neutropenia and thrombocytopenia as per Appendix 6 (Section 10.6) should be followed.
- Serum creatinine, creatine phosphokinase (CPK) and liver enzyme increase: follow corresponding algorithms as per Appendix 6 (Section 10.6).
- Cardiac arrhythmia (Atrial fibrillation): Any Grade 3 event (symptomatic, urgent intervention indicated; device [eg, pacemaker]; ablation; new onset).
- Suicidal risk as per C-SSRS: if a participant scores "yes" on items 4 or 5 of the Suicidal Ideation Section, or "yes" on any item of the Suicidal Behavior Section.

If needed, temporary treatment discontinuation can be considered by the Investigator or by the participant for any other reason, including due to any safety concerns because of disruption of the clinical trial due to a regional or national emergency declared by a governmental agency such as COVID-19 (Appendix 10 [Section 10.10]) or another illness or if there is a need for a prohibited concomitant medication. Treatment can be resumed later when it is considered safe and appropriate.

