10.8.5 Country-specific provisions for the US

Participants who previously discontinued IMP within 60 days of trial start due to the partial clinical hold and are now restarting IMP, will require liver function test monitoring at Weeks 2, 3, 4, 5, 6, 7, 8, 9, 10, 11, and 12 (M3), and then monthly for the next 9 months until M12. After that, the schedule visit timepoints per SoA (Section 1.3) will be resumed (ie, every 3 months), until the study end. Whenever a timepoint will coincide with a scheduled visit as per SoA, the full scheduled visit assessments will be performed instead of the liver monitoring testing alone.

10.8.6 Country-specific provisions for the US, Israel, and sites following FDA partial clinical hold conditions

In addition to refraining from medications that are moderate and potent inducers of CYP3A, participants must not take medications that are mild, moderate, and potent inhibitors of CYP3A or CYP2C8 hepatic enzymes throughout the conduct of the trial (see Appendix 9, Section 10.9).

Participants must refrain from consumption of grapefruit or grapefruit juice (due to inhibition of CYP3A4) from 5 days prior to intervention administration and throughout the treatment phase.

If medications that are mild, moderate, or potent inhibitors of CYP3A or CYP2C8 are clinically indicated, alternative options for non-CYP3A or non-CYP2C8 inhibitors should be considered, as medically appropriate. For participants not eligible for alternative options, IMP should be temporarily discontinued for the duration of treatment on these medications.

10.9 APPENDIX 9: EXAMPLE OF DRUGS WITH A POTENTIAL TO CHANGE SAR442168 METABOLISM OR ABSORPTION

The following drugs should not be taken during the study concomitantly with IMP due to their potential to change SAR442168 kinetics due to interaction with P450-mediated metabolism, being potent and moderate inducers of CYP3A or potent inhibitors of CYP2C8 liver enzymes (Table 8).

Additionally, participants in the US, Israel, and any other sites following FDA partial clinical hold conditions must not take medications that are mild, moderate, or potent inhibitors of CYP3A or CYP2C8 (Table 9).

Please note that the lists provided in Table 8 and Table 9 are not exhaustive and that the product information of drugs intended for concomitant use should be consulted.

Table 8 - Potent and moderate CYP3A inducers and potent CYP2C8 inhibitors

Potent CYP3A Inducers:		
Rifampin	Carbamazepine	

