#### **Observation** period

The observation periods for safety will be divided into 4 epochs:

- The screening (pre-treatment) period is defined as the period from the signed informed consent date up to first administration of the study intervention.
- The **treatment period** (ie, treatment-emergent (TE) period) is defined as the period from the first administration of study intervention to
  - The earlier of last administration of the study intervention + 10 days or first IMP in the LTS study for participants not receiving tolebrutinib OL treatment,
  - The first administration of tolebrutinib OL treatment for participants switching to OL therapy

- The **OL period** (ie, OL TE period), applicable only for participants switching to tolebrutinib OL treatment, is defined as the time from first administration of tolebrutinib OL treatment to the earlier of last administration of OL treatment + 10 days or first IMP in the LTS study
- The **post-treatment period**, if applicable, is defined as the period from the end of treatment period (or end of OL period, if applicable) to the participant's final post-treatment study contact date.

Summaries of OL period data will be presented by original randomized treatment group and overall.

The on-study period is defined as the time from randomization until the end of the study defined as the last scheduled visit for those who completed the study and the end-of-study date collected on electronic case report form (e-CRF) page "Completion of End of Study" for those who did not complete the study. If death is the end-of-study reason, date of death will be used.

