#### Additional analyses for drug-induced liver injury

The following additional analyses will be performed for drug-induced liver injury:

- Time to onset of the initial ALT or AST elevation (>3 x ULN) and total bilirubin elevation (>2 x ULN) during the treatment-emergent period will be analyzed using the KM method.
- The KM method will also be used to analyze time to onset of the following initial elevation ALT >3 x ULN, ALT >5 x ULN, ALT >8 x ULN, ALT >10 x ULN, AST >3 x ULN, AST >5 x ULN, AST >8 x ULN, AST >10 x ULN, total bilirubin >2 x ULN during the treatment-emergent period, respectively.
- A graph of the distribution of peak values of ALT versus peak values of total bilirubin during the treatment-emergent period will be provided.
- For each liver function test (eg, ALT), participants having experienced a PCSA (eg, ALT >5 x ULN) will be summarized using the following categories: Returned to baseline PCSA status (or returned to value ≤ULN in case of missing baseline) before last IMP dose, Returned to baseline PCSA status after last IMP dose, Never returned to baseline PCSA status, No assessment after elevation. This summary will be performed by categories of elevation ALT >3, >5, >10, >20 x ULN.

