#### 5.5 APPENDIX 5 ANALYSES SUPPORTING THE INTEGRATED SUMMARY OF SAFETY

Below are the additional analyses supporting the integrated summary of safety.

- Time to study intervention discontinuation for any reason (except switch to OL due to 6M-CDP) and due to AE using the KM method
- Exposure to study intervention by duration in participant years (≥24, ≥48, ≥72, ≥96, ≥120, ≥144, ≥168 weeks)
- Exposure to study intervention by subgroups in participant years
  - Age at screening (>40,  $\leq$ 40 years)
  - Sex (Male or Female)
  - Age by sex (>40 & male, >40 & female,  $\leq$ 40 & male,  $\leq$ 40 & female)
  - Race (White, Black or African American, Asian, Other)
  - Weight in kg ( $<70, \ge 70$  to  $<90, \ge 90$ )
  - BMI in kg/m^2 (<25,  $\geq 25$  to <30,  $\geq 30$ )
  - Baseline EDSS ( $<4, \geq 4$ )
  - Geographic region (US, non-US; Eastern Europe, Western Europe, North America, rest of the world [ROW])
  - Prior disease modifying therapy use (yes, no)
- Most frequent TEAEs sorted by relative risk and the corresponding forest plot
- Most frequent TEAEs sorted by risk difference and the corresponding forest plot
- Summary of TEAEs by primary SOC
- Summary of TEAEs by primary SOC, HLT and PT
- TEAEs leading to permanent study intervention discontinuation by exposure intervals (based on 24-week intervals)
- Incidence rate of post-treatment SAEs related to IMP
- Summary of TE AESIs by category, primary SOC and PT
- Summary of other TEAE groupings of interest by category, primary SOC and PT
- Incidence rate and relative risk ratio for TE AESIs and other selected AE groupings (COVID-19, suicidal behavior, malignancy) and the corresponding forest plot
- Incidence rate and risk difference for TE AESIs and other selected AE groupings (COVID-19, suicidal behavior, malignancy) and the corresponding forest plot
- Detailed summary for each AESI and other AE groupings
- Summaries of PTs occurring in at least 2/3/5% of participants on tolebrutinib and with a greater incidence compared to placebo by primary SOC and PT

- Boxplots and shift plots of the maximum values of ALT, AST, ALP and total bilirubin during treatment
- Incidence rates of TEAEs, TE SAEs, TEAEs leading to permanent study intervention discontinuation and AESIs/other AE group events by subgroups with corresponding forest plots

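### SAP exposure and the treatment-emergent period run through the partial clinical hold, so US participants who stopped and restarted are counted as exposed while off drug, and the liver time-to-event analyses state no time origin

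*SAP*

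**What the plan says.** **Exposure.** SAP 3.6.1: "Duration of IMP exposure is defined as last IMP administration date - first IMP administration date + 1 day, regardless of unplanned intermittent discontinuations". The result feeds the duration categories (24-week steps, ending at more than 96 weeks) and cumulative participant-years. SAP 5.5 adds "Exposure to study intervention by duration in participant years", with thresholds from 24 to 168 weeks.

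**Treatment-emergent period.** In SAP 3.1 it "is defined as the period from the first administration of study intervention to" this end point: "The earlier of last administration of the study intervention + 10 days or first IMP in the LTS study". For participants who switch to open label it ends at the first open-label dose. Interruptions are not carved out. Protocol 9.4.5 defines the same epochs.

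**Restarters.** Protocol 10.8.5 concerns "Participants who previously discontinued IMP within 60 days of trial start due to the partial clinical hold and are now restarting IMP". After restart they repeat the early liver-test schedule: weekly from Week 2 to Week 12, then monthly to Month 12. Amended Protocol 11 added this section, and the SAP says it is based on that amendment, yet it mentions neither the hold nor a restart.

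**Liver analyses.** SAP 3.6.3.1 plans Kaplan-Meier analyses of "Time to onset of the initial ALT or AST elevation (>3 x ULN) and total bilirubin elevation (>2 x ULN) during the treatment-emergent period", and of further ALT, AST and bilirubin thresholds. It does not say from which date time is counted.

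**Data.** Protocol 7.1.2: "For all temporary intervention discontinuations, duration should be recorded by the Investigator in the appropriate pages of the eCRF".

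**The concern.** Counting from first to last dose does little harm when gaps last days. The 10.8.5 restarters have at most about 60 days on drug, then an off-drug interval of unstated length, then a second course. Under the SAP the interval counts as exposure and anything arising in it is treatment-emergent. A participant who stops for good leaves the treatment-emergent period 10 days after the last dose. One who stops for just as long and then restarts never leaves it.

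Two kinds of output are exposed. The first is the exposure tables, above all the long-duration rows, where a participant with a few months on drug can appear as long-treated. The second is the timing of liver elevations. Drug-induced liver injury is the identified risk, Protocol 2.3 places the reported cases in Months 1 to 3 after starting, and the protocol repeats the early monitoring after restart. A curve that places a restarter's early elevation late would blur that pattern.

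**Working it through.** The plan gives no figure on this point, so there is nothing to reproduce. What follows applies its rule to hypothetical restarters.

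**Inputs from the documents.** The exposure rule and duration categories (SAP 3.6.1); at most 60 days on drug before the hold (Protocol 10.8.5, read as the participant's own start); a month of 28 days (SAP 1.1); mean treatment duration of 33 months, the low end of 33 to 36 (Protocol 4.2.1); 1100 participants (Protocol 9.2).

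**Assumptions.** 30 or 60 days on drug before the hold; a gap of 3, 6, 12 or 18 months (84, 168, 336 or 504 days); 84 to 336 days on drug after restart; 10 to 60 restarters.

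**1. Individual exposure.** SAP duration = before + gap + after. On-drug days = before + after. Selected cases:

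| Before / gap / after (days) | SAP days | On-drug days | Ratio | SAP category (weeks) | On-drug category (weeks) |
|---|---|---|---|---|---|
| 60 / 84 / 336 | 480 | 396 | 1.21 | >48 to 72 | >48 to 72 |
| 60 / 84 / 84 | 228 | 144 | 1.58 | >24 to 48 | up to 24 |
| 60 / 168 / 84 | 312 | 144 | 2.17 | >24 to 48 | up to 24 |
| 60 / 336 / 84 | 480 | 144 | 3.33 | >48 to 72 | up to 24 |
| 60 / 504 / 84 | 648 | 144 | 4.50 | >72 to 96 | up to 24 |
| 30 / 504 / 84 | 618 | 114 | 5.42 | >72 to 96 | up to 24 |

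The first and last rows are the extremes of the grid, so the range is about 1.2 to 5.4 times. The last two rows move up three categories.

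**2. Total participant-years, both arms.** Overstatement = n × gap / (N × 33 − n × gap), in months:

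- 10 restarters, 6 months: 60 / (36,300 − 60) = 0.17%
- 30 restarters, 12 months: 360 / (36,300 − 360) = 1.0%
- 60 restarters, 18 months: 1080 / (36,300 − 1080) = 3.07%

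**3. Liver timing, if counted from first dose.** For an elevation 8 weeks (56 days, Month 2.0) after restart, the plotted day = before + gap + 56:

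- Shortest case: 30 + 84 + 56 = day 170, Month 6.1
- Longest case: 60 + 504 + 56 = day 620, Month 22.1

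**The case against.** Much of the case on the other side stands.

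- **Convention.** First-to-last-dose counting is openly pre-specified, and SAP 3.6.1 pairs it with compliance (compliant days over planned days, with a category below 80%). Compliance may reveal off-drug time, but it corrects neither duration nor participant-years.
- **Time origin.** A reader might infer that the SAP times liver events from the wrong start. It names no start. First dose is the natural reading because the treatment-emergent period begins there, but that is an inference, and only elevations after restart would be affected. Scheduled liver tests are assigned by nominal visit (SAP Table 8), and how post-restart tests are labelled is not stated.
- **Open-label precedent.** The note to SAP Table 8 sets Day 1 to the first open-label dose for by-visit windows only. It is not a precedent for restarting a Kaplan-Meier clock.
- **Gap length.** A reader might infer a hold of about a year: planned 24-month recruitment from 23 October 2020, plus 60 days, gives 22 December 2022, which is 333 days before Amended Protocol 11 (20 November 2023). But actual recruitment may vary (Protocol 9.2), and no hold or restart dates are given.
- **Number of restarters.** Sixty is high. Uniform enrolment puts 1100 × 60/730 = 90 to 1290 × 60/672 = 115 participants worldwide in any 60-day window, and only US participants are concerned.
- **Event rates.** A reader might infer that the two arms' rates are materially pulled together. A 0.2% to 3% change in the total does not support that, and the split by arm is unknown. The main adverse-event tables use numbers and percentages of participants, with rates as additional output.
- **Broad reclassification.** It is tempting to call everything more than 10 days into any interruption off-treatment. Liver-enzyme rises themselves lead to temporary discontinuation (Protocol 7.1.2), so a later bilirubin peak could drop out of the peak ALT versus peak bilirubin plot.

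**Conclusion.** The point holds in a limited form. As written, the plan counts the hold as exposure and as treatment-emergent time for the 10.8.5 restarters, and nothing in the SAP corrects it. The distortion is potentially large for each restarter (1.2 to 5.4 times, up to three duration categories) and small for the trial total (about 0.2% to 3%). All of these sizes rest on assumed gaps, days on drug and numbers of restarters. Whether the phrase about stopping within 60 days of trial start means the participant's start or the study's is also unclear.

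For the liver Kaplan-Meier analyses the established defect is a missing time origin. The shift from Month 2 to Month 6 to 22 follows only if that origin is first dose. Safety analyses are descriptive and the primary efficacy analysis is unaffected. This is a worthwhile, inexpensive improvement rather than a threat to the trial's conclusions.

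**What to change.** 1. **SAP 3.6.1 and 5.5.** For participants restarting under Protocol 10.8.5, subtract the recorded hold interval from exposure duration and participant-years. Keep the first-to-last-dose figure as a secondary display.
2. **SAP 3.6.3.1.** State the time origin of the liver Kaplan-Meier analyses. Add a supplementary liver display for these restarters, timed from the restart dose.
3. **SAP 3.1.** Keep the existing treatment-emergent definition for the main tables, since it matches Protocol 9.4.5. Flag or list separately events that arise during the hold more than 10 days after the last pre-hold dose. Do not extend this to a general reclassification of events in all interruptions longer than 10 days.

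The cost is SAP wording, some programming and a slightly smaller stated exposure. No new data collection should be needed, because the protocol already asks for interruption durations to be recorded.

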#### **Treatment compliance**

A given administration will be considered noncompliant if the participant did not take the planned dose of treatment as required by the protocol, ie, once daily oral dose. No imputation will be made for participants with missing or incomplete data.

Percentage of compliance for a participant will be defined as the number of days that the participant was compliant divided by the total number of days of planned administration during the DB treatment period and OL period respectively.

Treatment compliance will be summarized quantitatively and categorically: <80%, ≥80%.

#### 3.6.2 Adverse events

#### General common rules for adverse events

All adverse events (AEs) will be graded according to National Cancer Institute Common Terminology for Adverse Events (NCI-CTCAE version 5.0, 27 Nov 2017) and coded to a lowerlevel term (LLT), preferred term (PT), high-level term (HLT), high-level group term (HLGT), and associated primary system organ class (SOC) using the Medical Dictionary for Regulatory Activities (MedDRA) version currently in effect at Sanofi at the time of database lock.

The AEs will be analyzed in the following 4 categories:

- Pre-treatment AEs: AEs that developed, worsened, or became serious during the pre-treatment period.
- Treatment-emergent adverse events (TEAE)s: AEs that developed, worsened, or became serious during the DB TE period
- OL AEs: AEs that developed, worsened, or become serious during the OL TE period
- Post-treatment AEs: AEs that developed, worsened, or became serious during the post-treatment period

Similarly, if occurring, deaths will be summarized in the pre-treatment, DB TE, OL, and post-treatment periods.

The primary focus of AE reporting will be on TEAEs. Pre-treatment, OL, and post-treatment AEs will be described separately.

An AE with incomplete or missing date/time of onset (occurrence, worsening, or becoming serious) will be classified as a TEAE unless there is definitive information to determine it is a pre-treatment, OL, or a post-treatment AE.

If the assessment of the relationship to IMP is missing for an AE, this AE will be assumed as related to IMP. If the severity is missing for 1 of the TE occurrences of an AE, the severity will be imputed with the maximal severity of the other occurrences. If the severity is missing for all the occurrences, the severity will be left as missing.

The AE tables will be sorted as indicated in Table 4.

AE presentation	Sorting rules
SOC and PT	By the internationally agreed SOC order and decreasing frequency of PTs a
AESI category and PT	By AESI category (protocol order) and decreasing frequency of PTs a
PT	By decreasing frequency of PTs a

a Sorting will be based on the tolebrutinib treatment group incidence, alphabetic order in case of equal frequency.

#### Analysis of all adverse events

The overview of TEAE will be generated presenting the number (%) of participants with:

- Any TEAE
- Any treatment emergent SAE
- TEAE leading to death
- Any TEAE leading to permanent study intervention discontinuation
- Any treatment emergent AESI
- Any TEAE considered by the investigator as related to study intervention

Similar summaries for OL emergent AEs will also be provided. An additional overview summary including the number and rate of events will be provided in the DB treatment period and OL period respectively.

The AE summaries of Table 5 will be generated with number (%) of participants experiencing at least one event.

Listings of SAEs from randomized participants, AEs from participants who are treated but not randomized, AEs leading to treatment discontinuation and severe AEs will be provided.

Type of AE	MedDRA levels
AII TEAE	Primary SOC and PT
	PT (incidence ≥2%)
Severe (grade ≥3) TEAEs	Primary SOC and PT
	PT
TEAE related to IMP as per Investigator's judgment	Primary SOC and PT
	PT
Treatment emergent SAE	Primary SOC and PT
	PT

